2. OVERVIEW OF STUDY DESIGN

This is a retrospective study of prospectively collected patient data with the use of secondary patient data from both paper and electronic patient files. All patients are treatment naïve at time of diagnosis. Both migalastat and ERT will be studied retrospectively. Also untreated patients will be studied by assessment of relevant clinical and laboratory variables. The analysis will originate at the time of diagnosis.

The patients have been followed for more than 20 years from 2001 until December 2023. All identified patients with Fabry disease, whether receiving specific Fabry medication or not, have been offered annual or biannual thorough workups including examinations of Fabry associated organ function and symptoms. The study will be carried out at the Danish National Fabry Centre, Department of Endocrinology, Copenhagen University Hospital.

All patients from the Danish National Fabry Centre will be included. Subgrouping is aimed at depending on available numbers: non-amenable, amenable, classic, non-classic, males, females, treated including type of treatment or untreated.

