13.1.1. Cox Proportional Analysis for Fabry-associated Clinical Events

The time to the first event is defined as time from the Analysis Start Date to the first composite FACE (primary interest), and to the first cardiac, cerebrovascular, renal clinical event, or death due to FACEs. For the primary analysis, patients who complete the study without an event, are lost to follow-up, discontinued the study, started dialysis, had a kidney or heart transplant, or after 30 days they changed/switched therapy (migalastat group) or after they start therapy (untreated group) will be censored. Describing effectiveness in migalastat treated population is of the main interest.

Treatment Switch

The primary analysis will address events that occur on therapy from the Analysis Start Date up until 30 days after the patient stops therapy or switches therapy. The events that happen afterwards will be excluded. For the patients untreated at time of diagnosis, the primary analysis will address events from the time of diagnosis until the patient starts a therapy. The events that happen afterwards will be excluded. An additional analysis will be performed:

1. An analysis that will address events that occur on therapy from the time of Analysis Start Date up until the patient stops therapy or patient switches therapy. For the untreated patients, the analysis will address assessments from the time of diagnosis until the patient starts a therapy. The events that happen afterwards will be excluded.

Primary Analysis Method

The ratio of the hazards of treatment groups will be checked to ensure that the hazard ratios are constant over time. Secondly, the assumption that each variable in the model makes a linear contribution will be checked.

The covariates will include:

- sex
- age at the Analysis Start Date as a continuous variable
- eGFR_{CKD-EPI} at the Analysis Start Date as a continuous variable
- LVMi at the Analysis Start Date
- previous history of cardiac, cerebrovascular, and renal clinical events (composite event) as related to Analysis Start Date
- Length of treatment for Fabry disease

If the measurements are not available, measurements prior to and closest to the Analysis Start Date will be used. In case that more than 50% of values are missing for a given covariate, it will be dropped from the analysis.

The estimate of hazard ratio for migalastat-treated/untreated along with the associated 95% CI will be calculated.

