15.4. Overall Survival

To assess the overall survival among all patients, a Cox proportional hazards model will be used, provided that the assumptions of Cox proportional hazard are met. The ratio of the hazards of treatment groups will be checked to ensure that the hazard ratios are constant over time. Secondly, the assumption that each variable in the model makes a linear contribution will be checked. Otherwise, Kaplan-Meier log-rank test will be used for this analysis.

Overall survival is defined as time from enrollment into the study until death due to any cause (event).

Covariates will include:

- sex
- enrollment age as a continuous variable
- enrollment eGFR as a continuous variable
- LVMi at enrollment
- time on treatment (ERT or migalastat overall)
- history of cardiac, cerebrovascular, and renal clinical events (a binary endpoint based on the composite event) prior to enrollment
- length of therapy for Fabry disease

If the measurements are not available, measurements prior to and closest to the Analysis Start Date will be used. In case that more than 50% of values are missing for a given covariate, it will be dropped from the analysis.

In the Safety Population where patients are analyzed based on the actual exposure, a Cox model run similarly to the analysis in Section [13.1.2](#) will be used but with 3 time-dependent variables indicating whether or not a patient is on migalastat, ERT, or untreated at time t. A patient may be in 1 or more treatment groups and a patient may be both left and right censored. For example, a patient that begins migalastat, stops at Month 3, begins ERT at Month 6, and then dies at Month 9 will be represented 3 times in the design matrix; the first for migalastat being right censored at Month 3, the second being for ERT left censored at Month 3 and right censored at Month 6, and finally, for untreated, being right censored at Month 6 and having an event at Month 9.

The estimate of hazard ratio for migalastat/ERT and migalastat/untreated along with the associated 95% CI will be calculated.

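### SAP 15.4 lists two undated treatment-time covariates for overall survival: at time zero they are empty, and counted over follow-up they would bring in immortal-time bias

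*SAP*

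**What the plan says.** SAP 15.4 sets the survival clock: "Overall survival is defined as time from enrollment into the study until death due to any cause (event". SAP 11.1 equates enrollment with the date of Fabry diagnosis. SAP 2 adds "All patients are treatment naïve at time of diagnosis", and the protocol's Method section agrees.

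The covariate list in 15.4 ties age, eGFR, LVMi and event history to enrollment. Two further entries carry no date: "time on treatment (ERT or migalastat overall" and "length of therapy for Fabry disease". Nothing says how they differ. A rule for unavailable values follows, in the same words as in 13.1.1: "If the measurements are not available, measurements prior to and closest to the Analysis Start Date will be used".

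SAP 15.4 then adds a second Cox model by actual exposure, modelled on 13.1.2, "but with 3 time-dependent variables indicating whether or not a patient is on migalastat, ERT, or untreated at time t". It ends: "The estimate of hazard ratio for migalastat/ERT and migalastat/untreated along with the associated 95% CI will be calculated". It does not say whether the covariate list enters the second model, or which model supplies these hazard ratios.

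The primary Cox model in 13.1.1 has a similar undated entry, "Length of treatment for Fabry disease", and the eGFR model in 13.7 repeats it. SAP 6.1 and SAP 10 provide for therapy dates and exposure before enrollment.

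**The concern.** A fixed covariate in a survival model has to be known at time zero. Treatment time counted after time zero is not: a patient must stay alive to accumulate it, so a high value is partly a record of having survived. Entered as a fixed term, it looks protective even when treatment does nothing. It also shifts any treatment-group coefficient in the same model, because group and treatment time are strongly related. The contrasts reported in 15.4, migalastat against ERT and against no treatment, are central to the study's purpose.

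**Working it through.** The plan gives no power, event count or target hazard ratio to reproduce (SAP 4 says the size was not determined statistically). The check is therefore the value each term takes under each meaning, followed by null simulation.

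**1. Value at time zero.** Enrollment = diagnosis (11.1), and nobody has been treated at diagnosis (2). Both terms equal 0 for all of about 115 patients. The two columns have rank 0, cannot be estimated, and leave every other coefficient unchanged.

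**2. Value over follow-up.** The only duration formula in the SAP is in 15.5: end of treatment minus start, plus 1 day. With therapy starting S years after diagnosis, no breaks, and death or censoring at T, this is L = max(0, T − S) in years, ignoring the one day. L grows with T. For example, take two patients with S = 2, one dying at T = 5 and one censored at T = 22. They enter with L = 3 and L = 20, although at year 5 each has received 3 years of therapy. If the two entries mean the same thing they are also aliased (rank 1 for two columns).

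**3. Therapy before enrollment.** SAP 6.1 uses therapy dates to derive a duration before enrollment, and SAP 10 tabulates prior exposure. This would be a valid baseline covariate. It contradicts SAP 2 and 11.1, and it can account for only one of the two entries.

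**4. Null simulation of meaning 2, treatment time alone.** Assumed: n = 115, diagnosis uniform over the first 20 of 22 years, censoring at year 22, constant death hazard h, 50% or 80% eventually treated with a median of 2 or 5 years to start, no stopping, no treatment effect; 400 runs per scenario. As a check on the set-up, expected deaths at h = 0.02 are 115 × [1 − (e^−0.04 − e^−0.44)/0.40] = 115 × 0.208 = 23.9, against 23.8 to 24.1 simulated.

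| h | treated; median start | fixed L: HR per year, rejection | L updated at t: HR per year, rejection |
|---|---|---|---|
| 0.01 | 50%; 2 y | 0.908, 18% | 0.993, 1.5% |
| 0.01 | 80%; 5 y | 0.863, 61% | 0.990, 2.2% |
| 0.02 | 80%; 2 y | 0.871, 99% | 1.009, 3.0% |
| 0.03 | 80%; 2 y | 0.864, 100% | 1.004, 4.5% |
| 0.03 | 80%; 5 y | 0.866, 99% | 1.002, 6.0% |

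Across all nine scenarios run, fixed L gave 0.863 to 0.908 with rejection of 18% to 100%; updated L gave 0.990 to 1.009 with 1.5% to 6.0%.

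**5. Null simulation of the group contrasts, fixed groups.** Assumed: n = 115; migalastat 15% or 30%, ERT 30%, the rest untreated; follow-up uniform on 0.5 to 7 years for migalastat and 1 to 22 otherwise; untreated patients start therapy at 0 or 5% per year; death rate 0.02 or 0.03; at least one death per group; 400 runs in each of 8 scenarios; other covariates omitted.

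| contrast | without L: median HR, rejection | with fixed L: median HR, rejection |
|---|---|---|
| migalastat/untreated | 0.99–1.39, 3–5% | 3.4–15.8, 30–68% |
| migalastat/ERT | 0.98–1.41, 2–5% | 0.22–0.38, 4.5–59% |

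The first error runs against migalastat and the second in its favour. The second depends on shorter migalastat follow-up, which is plausible because the protocol dates the drug's availability to 2016 and follow-up to 2001. With equal follow-up, migalastat/ERT is 0.96 to 1.07. If 30% stop early, the ratios are 1.7 to 2.8 and 0.46 to 0.52.

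**6. Time-dependent treatment state.** Under similar assumptions, adding fixed L gave 6.5 to 15.9 (migalastat/untreated) and 0.36 to 0.45 (migalastat/ERT). Time-updated L gave 0.87 to 1.06 and 0.96 to 1.15, with 2% to 4% rejection.

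**7. Primary model (13.1.1).** For migalastat against untreated, the Analysis Start Date is diagnosis (11.2), so a baseline value is 0 for all and the log hazard ratio does not move (difference below 1e-8). Total treatment to data cut-off gave 1% to 5% false rejection when events do not end treatment. Only measurement to event or censoring gave serious distortion (36% to 89%).

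**The case against.** The rule for unavailable values points to measurements before the Analysis Start Date. It appears in 15.4 as well as 13.1.1, so it supports a harmless baseline reading in both. That stands in part: it leans that way, but it governs unavailable measurements and does not date these two terms. Having two separate entries, one labelled as covering ERT or migalastat overall, makes an intended pair of zeros hard to believe.

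Nor are zero and follow-up treatment the only meanings. Duration before enrollment is a genuine third one, with support in 6.1 and 10. That stands, and makes part of the problem one of reconciling sections.

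A reader might infer that the promised survival hazard ratios will be biased. The documents do not support that. The sentence promising them directly follows the time-dependent model. That model is run like 13.1.2, which lists no covariates. If the ratios come from it without the list, they are untouched.

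The simulated sizes are also fragile. Under step 5's inputs there are on average only 1.2 to 3.7 migalastat deaths, and requiring a death in each group discards 2% to 29% of runs. This helps explain why the ratio without the term reaches 1.39 to 1.41 rather than 1.

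**Conclusion.** The point holds as a should-fix on a safety endpoint. Under the SAP's own definitions, two treatment-time entries in 15.4 are either empty at time zero or, if read as total exposure, condition on future survival. The third meaning could justify one of them at most, and only if SAP 2 and 11.1 are changed. Under the follow-up reading the direction is dependable: a spurious benefit per treatment year and, in a fixed-group model, bias against migalastat versus untreated and in favour of migalastat versus ERT when migalastat follow-up is shorter. The magnitudes rest on assumed death rates, group sizes and follow-up, and do not predict this study's results.

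A reader might also infer that the primary FACE comparison is compromised. The text does not support that: the natural baseline value in 13.1.1 is 0 for migalastat versus untreated and changes nothing. That term, and the one in 13.7, need a definition only.

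**What to change.** In 15.4, delete both treatment-time entries as fixed covariates. If cumulative exposure is of interest, enter it only as treatment accumulated up to time t in the interval-based model. State which covariates that model uses and which model yields the reported hazard ratios.

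Reconcile SAP 2 and 11.1 with 6.1 and 10. If patients treated before enrollment exist, keep one baseline term, *years of Fabry-specific therapy before enrollment*.

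In 13.1.1, define the term as therapy completed before the Analysis Start Date; in 13.7, before enrollment. Omit it where it is 0 for everyone. That covers migalastat versus untreated, and migalastat versus ERT if restricted to the initial treatment cohort named in 3.1. Where it is kept there is a price: with prior therapy assumed in 30% of migalastat patients, 11.6% to 51.8% of simulated fits failed to converge because pre-treated patients had few events. The SAP should say what is done then.

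The cost is SAP wording; no new data are needed.

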13.1.2. Interval Based Cox Proportional Analysis for Fabry-associated Clinical Events

In the interval-based time to event analysis will be used with 3 time-dependent variables indicating whether or not a patient is on migalastat, ERT, or untreated at time t . A patient may be in 1 or more treatment groups and a patient may be both left and right censored. For example, a patient that begins migalastat, stops at Month 9, begins ERT at Month 24, and then dies at Month 26 will be represented 3 times in the design matrix; the first for migalastat being right censored at Month 9, the second being for ERT left censored at Month 24 and right censored at Month 26, and finally, for untreated, being right censored at Month 9 and having an event at Month 24.

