15.1. Approach to Safety Analyses

As this is an observational study, patients may switch or stop therapies. In the Safety Population, analysis will present results based on the actual exposure, ie, treatment group at the time of the event (migalastat, ERT, or untreated). As patients can stop or switch therapy while enrolled in the study, they might be counted more than once in the analysis.

Serious adverse events will be analysed as described in Section 13 for the composite FACES.

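### The worked examples for the two time-dependent Cox models (SAP 15.4 and 13.1.2) contradict the SAP's own treatment-state rule and each other; 15.4 codes a death on ERT as an untreated event

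*SAP*

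**What the plan says.** SAP 13.1.2 (time to FACE) and SAP 15.4 (overall survival in the Safety Population by actual exposure) both specify a Cox model with "3 time-dependent variables indicating whether or not a patient is on migalastat, ERT, or untreated at time t". SAP 15.1 gives the matching attribution rule for safety: "analysis will present results based on the actual exposure, ie, treatment group at the time of the event". Section 15.4 presents its model as "a Cox model run similarly to the analysis in Section" 13.1.2, counts death from any cause as the event, and commits to a result: "The estimate of hazard ratio for migalastat/ERT and migalastat/untreated along with the associated 95% CI will be calculated".

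Each section then shows how one patient enters the design matrix.

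- **15.4.** The patient begins migalastat, "stops at Month 3, begins ERT at Month 6, and then dies at Month 9". The migalastat row is censored at Month 3. The ERT row is "the second being for ERT left censored at Month 3 and right censored at Month 6". The last row is described as "for untreated, being right censored at Month 6 and having an event at Month 9".
- **13.1.2.** The patient comes off migalastat at Month 9, starts ERT at Month 24 and dies at Month 26. The migalastat row is censored at Month 9. The ERT row enters at Month 24 and is censored at Month 26. The untreated row is described as right censored at Month 9, yet has an event at Month 24.

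**The concern.** With treatment defined as the state at time t, the rows must follow the calendar of the patient's history, and an event must fall in the row that is open when it happens. In 15.4 the ERT and untreated intervals look exchanged, and the death is placed on the untreated row although the patient is on ERT when it occurs. In 13.1.2 the untreated row has an event on the day ERT starts, when the history records no event.

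These are the only row layouts the SAP gives for the two models, and SAP 7.3 has programs checked for consistency with the plan. If the layouts are followed, deaths on ERT after an untreated gap would count as untreated deaths in the survival model, and person-time would be exchanged between the two states. Both enter the hazard ratios that 15.4 promises.

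**Working it through.** **Inputs.** The two histories and the coded rows come from SAP 15.4 and 13.1.2. The state rule comes from the same sections and the attribution rule from 15.1. Month 0 is taken as the start of migalastat, as both examples imply. An untreated row that is right censored and then has a later event is impossible if read literally, so the right-censoring month is read, in the plan's favour, as the month of entry.

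**Method.** Split each history into intervals (start, stop] by the state occupied, place the event in the interval that ends on the event date, and compare with the plan's rows.

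**15.4 (migalastat stopped at 3, ERT started at 6, death at 9)**

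| State | Plan's row | Months / events | By the time-t rule | Months / events |
|---|---|---|---|---|
| Migalastat | (0,3] censored | 3 / 0 | (0,3] censored | 3 / 0 |
| Untreated | (6,9] event | 3 / 1 | (3,6] censored | 3 / 0 |
| ERT | (3,6] censored | 3 / 0 | (6,9] event | 3 / 1 |

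Months under the wrong state: 3 (Months 3 to 6) + 3 (Months 6 to 9) = 6 of 9. The only event is also under the wrong state. Because survival counts death from any cause, the cause of death cannot change this.

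**13.1.2 (migalastat stopped at 9, ERT started at 24, death at 26)**

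| State | Plan's row | Months / events | By the time-t rule | Months / events |
|---|---|---|---|---|
| Migalastat | (0,9] censored | 9 / 0 | (0,9] censored | 9 / 0 |
| Untreated | (9,24] event | 15 / 1 | (9,24] censored | 15 / 0 |
| ERT | (24,26] censored | 2 / 0 | (24,26] event if a FACE death, otherwise censored | 2 / 1 or 2 / 0 |

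Months under the wrong state: 0 of 26. The example gives no cause of death, and SAP 13.1 and 13.1.1 count only deaths due to FACEs, so censoring the ERT row at Month 26 is right for a death from another cause. The untreated event at Month 24 has no basis either way, and the patient stays at risk for 26 − 24 = 2 months after it in a time-to-first-event model.

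**Do the two layouts agree?** Apply the 13.1.2 pattern to the 15.4 history. It gives ERT (6,9] censored and untreated (3,6] with an event at Month 6. Section 15.4 itself gives ERT (3,6] censored and untreated (6,9] with an event at Month 9. Only the migalastat row matches.

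**Readings that might rescue the examples**

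- *Literal right-censoring.* In 13.1.2 an untreated row of (0,9] would overlap migalastat for 9 months and leave Months 9 to 24 (15 months) uncovered.
- *The 30-day carry-over in 13.1.1.* At the SAP's 30.4 days per month, the gaps are 3 × 30.4 = 91.2 days and 15 × 30.4 = 456 days. Neither can be bridged by 30 days, and both patients are on ERT when they die.

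**The case against.** The strongest reply is that the slip in 15.4 may lie in the narrative. Its rows fit exactly a different patient: ERT from Month 3, stopped at Month 6, death off therapy at Month 9. That is possible, and it stands as a caution about where the error arose. It does not remove the conflict, because narrative and rows still disagree.

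Second, the examples only illustrate a rule that is stated correctly, and SAP 7.3 also requires independent program validation, senior statistical review and confirmation that the methods are valid. A careful programmer may well follow the rule. The harm is therefore conditional. But a correct program would then contradict the plan's own illustration, and one that matched the illustration would be wrong.

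Third, the reach is narrow. SAP 3.1 bases the formal primary analysis on the initial treatment cohort, 13.1.2 names no hazard ratio, and only patients who go from migalastat through an untreated gap to ERT are illustrated. All of this stands and limits the severity.

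Fourth, the time origin is unstated. Section 15.4 counts survival from enrolment, which SAP 11.1 sets at diagnosis, when SAP section 2 has all patients treatment naïve. Starting the migalastat row at Month 0 assumes treatment began then. This is fair, and the rewritten examples should name their origin.

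**Conclusion.** The concern holds and should be fixed before programming. In 15.4, 6 of the example patient's 9 months and the only death are coded under the wrong state for the history as narrated. In 13.1.2 no months are wrong, but one event is coded without basis. The two layouts cannot both be followed.

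The comparison rests on the two readings stated above: right-censoring on the untreated rows means entry, and Month 0 is the start of migalastat. The effect on the 15.4 hazard ratios cannot be sized, nor its direction given, because the number of patients with this sequence is not in the documents and other sequences are not illustrated. The primary model and the per-period descriptive analyses in 13.1.1, and the prevalence and incidence analyses in 13.2 and 13.3, do not use these layouts and are unaffected.

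**What to change.** Replace both examples with start-stop rows for the histories as narrated:

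- **15.4:** migalastat (0,3] event 0; untreated (3,6] event 0; ERT (6,9] event 1.
- **13.1.2:** migalastat (0,9] event 0; untreated (9,24] event 0; ERT (24,26] event 1 if the death is due to a FACE, otherwise censored at Month 26.

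If the sponsor meant a different history in 15.4, change the narrative so that history and rows agree. Add one sentence: an event belongs to the treatment state occupied on the event date, and each later row enters by delayed entry (left truncation). Each example should also name the date that Month 0 stands for.

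The cost is two corrected examples and one added sentence, plus a few words on the time origin. No new data and no new analysis are needed.
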